Study Design	This is an open, multi-center study using the oral ORMD-0801 insulin formulation in patients with NASH and confirmed type 2 DM. The study will consist of a Screening, Placebo run-in, Treatment Phase and End-of-Study Phase.
Study Endpoints	
The primary endpoint of this trial will evaluate safety of ORMD-0801 in patients with nonalcoholic steatohepatitis (NASH) and type 2 DM.
 
Secondary endpoints will evaluate the effectiveness of ORMD-0801 in reducing liver fat content in patients with NASH and type 2 DM by measuring the final and baseline differences in the MRI as liver function tests.

Summary of Assessments	
Safety Assessments:
 
Safety will be assessed by monitoring adverse events including hypoglycemia, physical exam, vital signs (blood pressure heart rate and oral temperature), ECG and clinical laboratory assessments.
 
Efficacy Assessments:

	Efficacy will be assessed by measuring the final and baseline differences in fat content obtained from MRI and Fibroscan results.
Duration of Participation	Screening Phase: up to 42 days prior to enrolment Placebo run-in Phase: 2 weeks Treatment Phase: 12 weeks End-of-Study (EOS): After completion of 4 weeks after end of treatment

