3.5 End-of-Study (EOS) (Week 16)/Early Discontinuations

The EOS Visit (Visit 9) will be conducted 4 weeks following the last scheduled treatment Visit. Patients will complete the following EOS evaluations:

- Concomitant medication
- Complete PE, only if the investigator deems it necessary.
- Weight
- ECG, only if the investigator deems it necessary.
- Vital signs (blood pressure, heart rate, oral temperature) will be measured in the sitting position after at least 5 minutes of rest, only if the investigator deems it necessary.

¹ HOMA = The Homeostasis Model Assessment

- Clinical laboratory evaluations (chemistry, hematology)
- Fasting blood glucose and fasting Insulin
- Blood lipids: Total cholesterol, LDL, HDL, Triglycerides
- Adiponectin
- HbA1C
- Urine pregnancy test
- AEs/SAEs assessment

Patients who are discontinued early from the study will complete the EOS evaluations at the time of early discontinuation.

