3.7 Self-Monitoring Fasting Blood Glucose and Patient Diaries

All patients will self-monitor fasting morning blood glucose levels three (3) times weekly during the run-in and treatment period. Monitoring must be performed at the same time each designated day (\pm 10 minutes) prior any caloric intake. Patients will be required to record the values in a patient diary and bring the diary to each clinic visit; Information recorded for the fasting blood glucose will be reviewed by the clinical research coordinator for completeness and transcribed onto CRF's. During the study, both fasting finger stick glucose and laboratory fasting plasma glucose will be obtained. Adverse events including hypoglycemia will be monitored from the self-monitoring blood glucose diary and recorded in the CRF.

If a fasting blood glucose measures greater than or equal to 270 mg/dL (15 mmol/L) during daily self-monitoring or during any in-clinic visit, the patient will be required to contact the clinic to report the value. The patient may be required to return for an unscheduled visit to the clinic for a repeat measurement of fasting blood glucose within one week after the original measurement. If the patient is invited for an unscheduled visit, blood will be drawn and sent to lab for plasma glucose determination. If the repeat measurement is also greater than or equal to 270 mg/dL, the patient will be discontinued from treatment with study drug and offered rescue medication. The patient will continue to be seen for all remaining study visits, if possible.

If a fasting blood glucose value is <70 mg/dL, the patient should drink 1 cup of orange juice or swallow 3-4 glucose tablets. The patient must check his blood sugar after 10 min and if the blood glucose level does not raise, the patients needs to drink another cup of orange juice or swallow 3-4 glucose tablets. Blood sugar must be checked again after 10 minutes. The patient must call to report this event to the study site and record all blood glucose levels in the diary.

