7.5 Recording Adverse Events

All adverse events experienced during the trial, regardless of relationship to study medication, must be recorded on the Adverse Event CRF from the time of patient consent until completion of patients End of Study visit (Visit 9). All serious adverse events will be collected through Visit 9. The Investigator must continue to follow all non-serious events possibly related to the study medication and all serious adverse events until they resolve or until the Investigator assesses them in writing as chronic or stable.

Regardless of relationship to study medication, the event must be recorded on the Adverse Event CRF. Adverse event documentation should include the following information:

- Standard medical terminology for the AE
- Description of adverse event
- Date and time of onset
- Date and time of resolution of the adverse event
- Whether or not the event is ongoing
- Severity of the event
- Relationship between the adverse event and the investigational product
- Description of any actions taken (e.g., medications, treatments)
- Outcome of the AE
- Whether or not the effect was serious and/or unanticipated

Whenever possible, a diagnosis should be given when signs and symptoms are due to common etiology (e.g., cough, runny nose, sneezing, sore throat, and head congestion should be reported as "upper respiratory infection"). For the purposes of this study, hypoglycemic events will be considered adverse events and should be recorded in source and CRF records.

When a diagnosis is not available, each adverse event should be reported separately. For example, "nausea and vomiting" should be split into two separate events.

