8.2 Safety Evaluation

8.2.1 Adverse Events

AEs will be coded using the most current version of MedDRA. The severity of AEs will be graded according to NCI CTCAE version 4.03. AEs will be regarded as “pretreatment” if they occur during the Placebo run-in period. TEAEs are defined as any AE that starts or increases in severity after the first dose of IMP at Visit 3.

The incidence of TEAEs will be tabulated by MedDRA preferred term, system organ class, treatment group, severity, and assigned relationship to IMP. The incidence for each TEAE will be provided as the total number of subjects that experienced the TEAE, as well as the percentage of the population that this represents. If a TEAE is reported more than once for a given subject, the greatest severity and the worst-case attribution will be presented in the summary tables.

TEAEs will be listed for individual subjects, along with information regarding onset and end dates, onset time where available, severity, seriousness, relationship to IMP, action taken, and outcome. A similar listing will be prepared for the pretreatment AEs.

Pretreatment AEs and TEAEs that lead to withdrawal from the study will be separately listed and summarized. Similarly, separate tabulations and listings will be prepared for pretreatment and treatment-emergent SAEs.

Descriptive statistics will be generated as appropriate (i.e., frequency for categorical data). Inferential statistical analysis comparing the AE data between Active treatment and Placebo is not planned.

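### Placebo run-in adverse events are mostly only listed, while treatment-emergent events are crude percentages over 12 to 16 weeks, so the two periods are not summarised on a comparable scale

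*Combined protocol and SAP*

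**What the plan says.** The Synopsis gives the structure: "The study will consist of a Screening, Placebo run-in, Treatment Phase and End-of-Study Phase". It gives the lengths as "Placebo run-in Phase: 2 weeks Treatment Phase: 12 weeks". Section 3.5 adds the off-treatment follow-up: "The EOS Visit (Visit 9) will be conducted 4 weeks following the last scheduled treatment Visit". Under Section 7.5, adverse events are recorded from consent until Visit 9.

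Section 8.2.1 calls events pretreatment "if they occur during the Placebo run-in period". An event is treatment-emergent if it begins or worsens after the first dose at Visit 3, and no end to that window is given. Treatment-emergent events are tabulated by system organ class, preferred term, severity and relationship, as the number and percentage of subjects. For run-in events in general the output is this: "A similar listing will be prepared for the pretreatment AEs". Two categories, serious events and events leading to withdrawal, are summarised for both periods, in separate outputs. On comparison the section says only: "Inferential statistical analysis comparing the AE data between Active treatment and Placebo is not planned".

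For glucose, Section 3.7 states: "All patients will self-monitor fasting morning blood glucose levels three (3) times weekly during the run-in and treatment period".

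**The concern.** With no concurrent control, the run-in is the one place where the same patients take the same number of capsules, at the same time of day, without active drug. It offers a rough view of the background event rate in a study whose primary endpoint is safety.

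Declining a formal test does not settle the matter, because the difficulty lies in the descriptive scale. The percentage of subjects with at least one event grows with the length of observation. A 2-week percentage and a 12- to 16-week percentage therefore differ even when nothing has changed. For serious events and withdrawals, the planned outputs will contain both figures with no stated exposure adjustment. For everything else, including hypoglycaemia (the event of special interest in Section 7.3), a reader who wants the run-in figure must count it from a listing and then meets the same mismatch.

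**Working it through.** **Inputs from the documents.** Run-in 2 weeks and treatment 12 weeks (Synopsis); follow-up 4 weeks (Section 3.5); up to 40 patients (Section 8.1). The plan states no adverse event rate and no figure for this comparison, so there is nothing of its own to reproduce.

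**Assumptions.** The 2-week incidence p is varied from 1% to 30%. The event rate is constant, the drug has no effect, and all 40 patients are followed throughout.

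**Windows.** 12/2 = 6 and 16/2 = 8, so time at risk after Visit 3 is 6 to 8 times that of the run-in.

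**Crude incidence over t weeks** = 1 − (1 − p)^(t/2). For p = 10%: 1 − 0.9^6 = 46.9% at 12 weeks and 1 − 0.9^8 = 57.0% at 16 weeks.

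| Run-in, 2 weeks | 12 weeks | Ratio | 16 weeks | Ratio |
|---|---|---|---|---|
| 1% | 5.9% | 5.9 | 7.7% | 7.7 |
| 2% | 11.4% | 5.7 | 14.9% | 7.5 |
| 5% | 26.5% | 5.3 | 33.7% | 6.7 |
| 10% | 46.9% | 4.7 | 57.0% | 5.7 |
| 20% | 73.8% | 3.7 | 83.2% | 4.2 |
| 30% | 88.2% | 2.9 | 94.2% | 3.1 |

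At p = 10%, 40 patients would give 4 affected in the run-in against about 19 (12 weeks) or 23 (16 weeks). The ratio is largest for rare events, and serious events, which are summarised for both periods, would usually be rare.

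**Does the direction depend on a constant rate?** If the weekly rate halved after the run-in, p = 10% would still give 1 − 0.9^3 = 27.1% and 1 − 0.9^4 = 34.4%. For the crude percentages to match, the rate must fall to 1/6 (12 weeks) or 1/8 (16 weeks) of its run-in value.

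**Per patient-week.** Run-in 40 × 2 = 80; treatment 40 × 12 = 480; follow-up 40 × 4 = 160; total after Visit 3, 640. With a constant rate and no drug effect, the expected rate ratio is 1.

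**Precision of that ratio** (approximate 95% interval around a true ratio of 1, 12-week window, independent events): multiply and divide by exp(1.96 × √(1/E₀ + 1/E₁)), where E₀ and E₁ are expected events. At p = 10% the weekly rate is −ln(0.9)/2 = 0.0527, so E₀ = 4.2 and E₁ = 25.3, giving 0.36 to 2.8. At p = 5% the interval is 0.23 to 4.4, and at p = 20% it is 0.49 to 2.0.

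**Glucose readings.** Scheduled fasting readings are 3 × 2 = 6 in the run-in and 3 × 12 = 36 on treatment. Sections 3.7 and 7.5 also bring in events found at symptom-triggered finger-sticks and at rechecks, so all hypoglycaemia divided by scheduled readings would mismatch numerator and denominator.

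**The case against.** The plan does not set all run-in and treatment-emergent events side by side. A reader might infer that the planned tables will themselves suggest harm. The documents do not support that: outside serious events and withdrawals there is no run-in table to compare with, and even those two outputs are separate. The misreading needs someone to make the comparison.

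A reader might also infer that the run-in data go unused. They do not: each event is listed with detail similar to that for treatment-emergent events, and the two most important categories are summarised. Section 8.2.1 also allows frequencies as appropriate, the Synopsis promises extent of exposure, and Section 8 defers detail to a statistical analysis plan. No separate plan text was available for this review, so a run-in table could be specified there.

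Nor does it follow that background events cannot be told from drug-related ones. Section 7.6 requires a causality assessment and Section 8.2.1 tabulates by relationship. Those judgements are made open-label, which limits them but does not make them worthless.

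Finally, the two periods are not observed identically. The run-in spans Visit 2 to Visit 3, whereas treatment has visits at weeks 1, 2, 4, 8 and 12. Under Section 6.5.5 safety laboratory tests are not drawn at Visit 2. The order of periods is fixed. Patient-week rates correct for length of observation and for none of these.

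All of this stands and limits the point. What remains is that Section 8.2.1 specifies neither a general run-in summary nor a time-at-risk denominator.

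**Conclusion.** The point holds as a modest gap in presentation. For the primary safety question, the trial's only within-patient placebo period is not summarised on a scale comparable with the 12 to 16 weeks that follow. Wherever the two periods are both summarised, or a reader compares them, crude incidence after Visit 3 would be about 3 to 8 times higher with no drug effect. That size rests on an assumed 2-week incidence of 1% to 30%, a constant rate and complete follow-up. The direction would change only if the rate fell by more than about 6- to 8-fold after the run-in. Correcting the scale makes a descriptive comparison fair as to time at risk. It does not make it precise, and it cannot establish or exclude a drug effect. The issue is minor and worth fixing because it is cheap.

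**What to change.** In Section 8.2.1:

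- Tabulate run-in adverse events by system organ class and preferred term, as for treatment-emergent events.
- State when the treatment-emergent window ends, and the denominator for each period. The denominator needs care: the safety population in Section 8.1.1 rests on receiving IMP, a term that Section 7.9 applies to active or placebo, while treatment-emergent events start at Visit 3.
- Report subjects with events, and events per patient-week, separately for run-in, treatment and the 4-week follow-up, including hypoglycaemia per patient-week. If hypoglycaemia is also given per reading, count only events found at scheduled fasting readings.
- Give confidence limits that allow for repeat events within a patient, or limits on the proportion of subjects with at least one event. Plain Poisson limits treat repeat events as independent and can be too narrow. Do no test.
- Label the comparison descriptive. Note that about 80 run-in patient-weeks give an imprecise rate, and that fixed order and differing visit and laboratory schedules remain.

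The cost is a few more table columns from data already collected, with no change to visits or sample size. The downside is a run-in rate too imprecise to carry much weight, which the label must make plain.

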If three or more fingerstick glucose values of <50 mg/dL (2.78 mmol/L) are observed within 12 hours subsequent to administration of study drug without a reasonable explanation (such as increased physical activity and/or skipped meal), the patient will be discontinued from treatment with study drug and rescued with glucose administration (20g of glucose tablets) which will be available at all times at the study site. This information will be recorded in the patient's diary and

the patient will be instructed to contact the study site if this occurs. The patient will continue to be seen for all remaining study visits.

Sites will instruct patients to immediately perform a finger stick glucose measurement if any symptoms occur that may be related to hypoglycemia (e.g., weakness, dizziness, shakiness, increased sweating, palpitations, or confusion), and to avoid delay in treating these symptoms. The measurements will be recorded in the patient diary. Patients will always carry glucose tablets with them and ingest 3-4 tablets if hypoglycemia occurs.

Hypoglycemia and associated symptoms (e.g., weakness, dizziness, shakiness, increased sweating, palpitations, or confusion), have been associated with insulin administration, including ORMD-0801.

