In the event that a subject discontinues the study prior to completion, the date the subject is withdrawn and the reason for discontinuation will be recorded in the source documents and CRF. Although a subject will not be obliged to give his/her reason for withdrawing prematurely, the Investigator will make a reasonable effort to obtain the reason while fully respecting the subject's rights.

All subjects who are randomized and treated (i.e., received any amount of IMP) will be included in the safety analyses. Thus, every effort will be made to contact any subject who fails to attend any follow-up appointments/contacts, in order to ensure that he/she is in satisfactory health. If a subject withdraws from the study as a result of meeting discontinuation criteria after the start of IMP administration, reasonable efforts should be made to have the subject return for the early withdrawal evaluations (Section 3.5). Any subject withdrawn due to a suspected IMP -related AE should be followed until resolution or stabilization of the event.

If a subject becomes pregnant, IMP will be discontinued immediately, and the subject will be referred to an obstetrician/gynecologist experienced in reproductive toxicity for further evaluation and counseling. The subject will be followed until delivery or other termination of pregnancy for outcome.

Subjects may choose to withdraw authorization to use and disclose their PHI. Such withdrawal of authorization must be made to the Investigator in writing. Any PHI collected by the Investigator prior to the date of such withdrawal will continue to be used and disclosed.

The Sponsor has the right to terminate this study, and the Investigator/Investigational Site has the right to close the site, at any time, although this should occur only after consultation between involved parties. The Investigator or representative will notify the IRB in writing of a premature termination of a study or closure of Investigational Site or of a temporary halt of the study, including the reason of such an action and will send a copy of the notification to the Sponsor.

Events that may trigger premature termination of a study or closure of an Investigational Site include, but are not limited to, a new toxicity finding, a request to discontinue the trial from a regulatory authority, non-compliance with the protocol, GCP violations, slow recruitment/low enrollment, or change in development plans for the IMP.

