7.5.1 Routine Reporting of Adverse Events

All AEs, whether or not associated with the IMP that are observed by the Investigator, other Investigational Site personnel, or those reported by the subject will be recorded in the subject's source documentation and on the AE page of the CRF. Copies of the SAE CRF pages or an SAE listing generated based on the CRF pages will be submitted to the Sponsor at regularly scheduled intervals to allow the Sponsor to meet expedited regulatory reporting requirements under 21 CFR 312.32 and regular regulatory reporting requirements under 21 CFR 312.33.

For each AE, the following information will be entered in the CRF:

- Medical diagnosis of the event in standard medical terminology (if a medical diagnosis cannot be determined, a description of each sign or symptom characterizing the event);
- Date of onset of any new AE or worsening of a previously observed AE. For the days when the subject is in the clinic (Visit 2 to Visit 9), the time (based on a 24-hour clock) of onset should be recorded if available;
- Date of resolution of the event (or confirmation ongoing). For the days when the subject is in the clinic (Visit 2 to Visit 9), the time (based on a 24-hour clock) of resolution should be recorded if available;
- Whether the event is serious (per definition in Section 7.4), and if so, the reason it is considered serious;
- Severity of AE (per definition in Section 7.7);
- Assessment of the attributability of the AE to the IMP [per definition in Section 7.5];
- Whether the event is expected (per definition in Section 7.8);
- Action taken in treating the AE (including concomitant medications or therapies administered) and/or change in the IMP administration or dose (including whether the IMP was temporarily interrupted or discontinued);
- Outcome of AE (per definition in Section 7.9).

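### The only planned discontinuation summary counts withdrawal from the study, so patients taken off ORMD-0801 under the Section 3.7 glucose rules but kept in follow-up are not counted in it

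*Combined protocol and SAP*

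**What the plan says.** Section 8.2.1 plans a table of all treatment-emergent events: "The incidence of TEAEs will be tabulated by MedDRA preferred term, system organ class, treatment group, severity, and assigned relationship to IMP". It also plans separate tabulations and listings of serious events, and a by-subject listing that includes "severity, seriousness, relationship to IMP, action taken, and outcome". On discontinuation it says: "Pretreatment AEs and TEAEs that lead to withdrawal from the study will be separately listed and summarized".

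Section 3.7 contains two rules that stop study drug:

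- **High glucose.** If a repeat fasting value is again at or above 270 mg/dL, "the patient will be discontinued from treatment with study drug and offered rescue medication". The rule continues: "The patient will continue to be seen for all remaining study visits, if possible".
- **Low glucose.** After at least three fingerstick readings under 50 mg/dL in the 12 hours following a dose, with no reasonable explanation, "the patient will be discontinued from treatment with study drug and rescued with glucose administration". This patient also continues with all remaining visits.

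Section 4.3 requires, for a subject who discontinues the study early, that "the date the subject is withdrawn and the reason for discontinuation will be recorded in the source documents and CRF". For each adverse event, Section 7.5.1 has the CRF capture "change in the IMP administration or dose (including whether the IMP was temporarily interrupted or discontinued"). The synopsis (Statistical Methods) promises disposition, extent of exposure, and study termination or withdrawal information.

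**The concern.** The protocol separates stopping the drug from leaving the study, but the discontinuation summary follows only the second. The patients it misses include those for whom the protocol itself requires the drug to be stopped because of a glucose value.

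The product is an insulin, safety is the primary endpoint, and hypoglycemia is the adverse event of special interest (Section 7.3.1). How many patients had to stop the drug because of glucose is therefore a main tolerability result. If Section 8.2.1 is followed as written, the report can show a low discontinuation count while other patients stopped the drug under Section 3.7.

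**Working it through.** The plan states no figure to reproduce: there is no alpha, power, effect size or expected event rate, and Section 8.1 says that the study is not powered. The check follows a patient stopped under each Section 3.7 rule through the protocol's records and outputs.

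**1. Are the two states distinct in the protocol?** Yes. Section 4.3, in its rule on replacing subjects, names those withdrawn after treatment and those who discontinue study drug in separate sentences. Section 3.7 keeps patients in follow-up after the drug stops.

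**2. Where each type of stop appears**

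| Step | Low-glucose stop | High-glucose stop |
|---|---|---|
| Adverse event by rule? | Yes (Section 7.5) | No specific rule. Reportable under Section 7 (worsening of a pre-existing condition) and 7.2 (abnormal laboratory findings), but Section 8.2.2 leaves laboratory changes to the investigator's judgment |
| Drug stop captured on the adverse event CRF? | Yes, under action taken (Section 7.5.1) | Only if an adverse event is reported |
| By-subject listing (Section 8.2.1)? | Yes | Only if an adverse event is reported |
| TEAE incidence table? | Event counted, drug stop not | Event counted only if reported, drug stop not |
| Summary of events leading to discontinuation? | No, because the patient has not left the study | No, for the same reason |
| Required date and reason for stopping drug (Section 4.3)? | No, covers study discontinuation only | No, covers study discontinuation only |
| Other trace | Dosing records (Section 5.5), exposure (synopsis) | Dosing records (Section 5.5), exposure (synopsis) |

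Neither stop reaches a planned count of drug discontinuations. For a high-glucose stop without an adverse event, dosing and exposure data would show that dosing ended, but nothing requires the reason to be recorded.

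**3. Does the per-protocol set expose these patients?** Not reliably. Section 8.1.1 requires 80% to 120% of the product and completion of all visits. If the 80% is taken over 12 weeks (an assumption), 0.80 × 84 days = 67.2 days. A fully compliant patient stopped after about day 68 who attends every visit could still qualify.

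**4. Cross-reference.** Section 5.3 sends the reader to Section 4.3 for discontinuation criteria. The glucose rules are in Section 3.7 and are not listed in Section 4.3, so a CRF built from the Section 4.3 list would have no code for them.

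**5. Scale.** One patient is 1/40 = 2.5 percentage points if the maximum of 40 (Section 8.1) are all treated, and more if fewer are. As an illustration with assumed counts: one study withdrawal for an adverse event plus two to four drug stops under Section 3.7 would be summarised as 1/40 = 2.5%, when 3/40 = 7.5% to 5/40 = 12.5% had stopped the drug.

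**The case against.** A reader might infer that the safety tables cover only events that lead to withdrawal. They do not: all treatment-emergent events and all serious events are tabulated, and only the discontinuation subset is restricted.

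A reader might also infer that glucose-triggered stops go unrecorded. For low glucose the documents rule this out, because hypoglycemic events must be recorded as adverse events and the CRF shows whether the drug was stopped. For high glucose, every participant has type 2 diabetes, so a repeat value that forces a drug stop could well be reported as worsening. Glucose values are transcribed to the CRF, dosing is recorded there and returned capsules are counted, concomitant drugs are recorded with an indication (Section 6.6), and exposure is reported. What is missing is narrower: a required date and reason for the drug stop when no adverse event is reported.

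Two further arguments deserve weight. With at most 40 patients in a descriptive single-arm study, a listing can be read line by line, so a table row is partly a matter of presentation. That is fair for low-glucose stops, but a listing is still not a count, and a high-glucose stop may not be in it. Secondly, Section 8 defers detail to a statistical analysis plan. No separate plan text is in the supplied document, so the gap is shown for this text only. A later plan could add the table, but it could not recover a reason for stopping that the CRF was never required to collect.

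**Conclusion.** The point holds as a gap in reporting, with a smaller gap in data collection. On the supplied text, patients taken off ORMD-0801 under either Section 3.7 rule who remain in follow-up are left out of the only planned discontinuation summary, and no other output counts them. The data-collection gap is confined to high-glucose stops that the investigator does not report as adverse events.

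The size is 2.5 percentage points per uncounted patient, assuming all 40 are treated. How many patients would be affected is unknown, because the documents give no event rate; the range of 7.5% to 12.5% rests on assumed counts. The conclusion also assumes that withdrawal from the study in Section 8.2.1 means what it means elsewhere in the protocol, that is, leaving the study and not merely stopping the drug.

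**What to change.** - **Section 8.2.1:** list and summarise treatment-emergent events leading to permanent discontinuation of ORMD-0801, with or without study withdrawal. Keep events leading to study withdrawal as a separate row.
- **Section 4.3 and the CRF:** require last-dose date and reason for every permanent drug stop, with the two existing Section 3.7 triggers as coded reasons.
- **Disposition table:** show three groups (completed drug; stopped drug and stayed in the study; left the study), so that a high-glucose stop appears even without an adverse event.
- **Sections 5.3, 4.3 and 3.7:** reconcile the reference to discontinuation criteria with the place where the glucose rules stand.

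The stopping rules themselves are untouched. The cost is one added CRF item and one or two table rows. The reported discontinuation rate may look less favourable.
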